5.1.4 Same-session MR-only Simulation and Fraction 1 Adaptive Treatment Planning

All patients will be planned for a two or five fraction treatment course. Prescription dose will be at the discretion of the treating physician but will be subject to hard constraints based on the treatment site. Dose volume histogram (DVH) information for the target volumes and surrounding critical structures is mandatory. This is to assist in interpreting outcome, including morbidity. Coverage goal will be for 95% of the volume to be covered by 95% of the dose, although in situation where a critical structure is violated, reduction of dose will be allowed in areas of overlap. For specific hard constraints and optimization parameters, see Section 5.1.5.

Prior to day of first fraction and creation of the clinical plan, each patient will be tentatively pre-planned based on their diagnostic MRI volumetric image set obtained prior to study enrollment. A bulk density override method will be used to manually assign relative electron density values to the diagnostic dataset for the purpose of dose calculation and setting up initial plan parameters. For example, voxels representing the patient's bones will be assigned an average bone density, voxels representing fat will have a different density assignment, etc. This "pre-plan" will allow for efficient same-session simulation and clinical planning on the day of treatment. On treatment day one, another volumetric MRI image will be obtained on the treatment machine itself, and the plan will be adjusted based on anatomy and patient habitus of the day. Previously assigned density values will be reviewed and adjusted if needed, after which the final clinical treatment plan will be created.

In tandem with the clinical planning process above, a novel exploratory non-clinical density override method will be used for comparative dosimetry. In this method, the density values are assigned on a voxel-by-voxel basis automatically, rather than as a manual bulk override as clinically used, via a machine-learning algorithm. This will not be used for clinical decision making or affect treatment planning. The data gathered will be used to improve the MRI-only planning process in the future.

5.1.5 SMART Dose Constraints

These shall function as hard constraints in treatment planning, and coverage will be sacrificed to meet these constraints. All listed constraints are for 2 fraction treatment (Table A) or 5 fraction treatment (Table B), which are both acceptable

course fractionations for this study. Adaptive plans will be evaluated under the assumption that the delivered adaptive plan would meet all hard constraints for 2 or 5 fractions with stable anatomy. For example, on a given day, in a 5-fraction course, the maximum cord dose (to 0.5 cc) will be 5 Gy (extrapolate to maximum dose 25 Gy over 5 fractions).

Table A

Organ-at-Risk	Volume	Constraint (Gy)	Other
PRV spinal cord subvolume (thecal sac or 2mm)	<0.03cc	17	-
PRV Cauda Equina	<0.03cc	17	-
Sacral Nerve S1-5	<0.03cc	26	-
Esophagus	<0.03cc	20	-
Pharynx/Larynx	<0.03cc	20	Mean < 9Gy
Brachial Plexus	<0.03cc	21.5	-
Parotid	-	-	Mean < 7Gy
Rectum	<0.03cc	20	-
Trachea	<0.03cc	20	-
Rib	<5cc	45	57
Skin	<10cc	20	-
Stomach	<0.03cc	20	-
Duodenum	<0.03cc	20	-
Small Bowel	<0.03cc	20	-
Large Bowel	<0.03cc	20	-
Kidneys	<0.03cc	26	Mean < 6Gy
Lungs (combined)	-	-	V10Gy < 10% V5Gy < 35%
Liver	-	-	Mean < 8Gy

Table B

Organ-at-Risk	Volume	Max Dose to Volume (Gy)	Max Point Dose* (Gy)
Brainstem (not medulla)	<0.5cc	23	31
Spinal Cord and medulla	<0.35cc	22	28
	<1.2cc	15.6	-
Spinal Cord Sub-volume (5-6mm above and below level treated)	<10% of sub-volume	22	28
Cauda Equina	<5cc	30	31.5
Sacral Plexus	<5cc	30	32
Esophagus	<5cc	19.5	35
Brachial Plexus	<3cc	27	32.5
Heart/Pericardium	<15cc	32	38

Great Vessels	<10cc	47	53
Trachea and Large Bronchi	<5cc	32	40
Rib	<5cc	45	57
Skin	<10cc	36.5	38.5
Stomach	<5cc	26.5	35
Duodenum	<5cc	18.5	26
Small Bowel	<30cc	20	32
Large Bowel	<20cc	28.5	40
Rectum	<35.cc <20cc	50 32.5	55 -
Ureter	-	-	45
Bladder Wall	<15cc	20	38
Penile Bulb	<3cc	30	-
Femoral Heads	<10cc	30	-
Kidneys	mean	18	-
Lungs (combined)	1500cc 1000cc	12.5 13.5	- -
Liver	700cc	21	-

*Max point dose defined as dose to ≤ 0.035 cc.

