5.1.1 Dose, Fractionation

Radiotherapy will consist of stereotactic body therapy, to be given over either a two or five fraction course, delivered once daily or once every other day for a period of one to two weeks, for a total of two or five treatments (depending on whether a 2 or 5 fraction course is selected). Patients will be planned for an initial prescription dose at the discretion of the treating physician, delivered in two or five total fractions to the PTV, with dose adaptation based on safety constraints that are already approved of to prevent OAR injury. Suggested dose prescriptions are 24 Gy in 2 fractions or 35 Gy in 5 fractions.

[figure not shown]

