5.1.6 Adaptive Treatment Planning at Subsequent Fractions

After delivery of the first treatment fraction using a same-session MR-only simulation and treatment with SMART, the treating physician will evaluate the patient's individual anatomy at subsequent treatment fractions to determine if further daily adaptive planning is indicated. Treatment plan re-optimization will be performed for dose adaptation if it is determined that the patient's anatomy necessitates dose adaptation with the goal of sparing of normal structures (i.e., not violating the predetermined hard constraints based on safety constraints that are already approved of for routine, clinical use).

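### The 2-fraction rib limit in Table A repeats the 5-fraction row of Table B unchanged and would not constrain a 24 Gy plan

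*Combined protocol and SAP*

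**What the plan says.** Section 5.1.5 gives two tables of organ-at-risk limits, one per schedule: "All listed constraints are for 2 fraction treatment (Table A) or 5 fraction treatment (Table B". Both have the same force: "These shall function as hard constraints in treatment planning, and coverage will be sacrificed to meet these constraints".

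The rib row and the skin row below it read as follows.

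- Table A (2 fractions): "Rib <5cc 45 57 Skin <10cc 20"
- Table B (5 fractions): "Rib <5cc 45 57 Skin <10cc 36.5 38.5"

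The column headings differ. In Table B the two rib figures fall under the dose to the stated volume and the maximum point dose. Table A has one dose column and a column headed *Other*, and the 57 sits in the latter with no unit or label.

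Section 5.1.1 on dose: "Suggested dose prescriptions are 24 Gy in 2 fractions or 35 Gy in 5 fractions". These are suggestions only. Section 5.1.4 adds: "Prescription dose will be at the discretion of the treating physician but will be subject to hard constraints based on the treatment site".

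Section 5.1.5 also shows how a course limit becomes a daily one: "For example, on a given day, in a 5-fraction course, the maximum cord dose (to 0.5 cc) will be 5 Gy", which it extrapolates to 25 Gy over five fractions. Section 5.1.6 says where the limits come from, describing adaptation as "not violating the predetermined hard constraints based on safety constraints that are already approved of for routine, clinical use".

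**The concern.** A limit for two large fractions should not normally equal the limit for five smaller ones, and Table A is otherwise built on that principle. One organ with identical figures in both tables, one of them under a heading that does not describe it, suggests that the 5-fraction row was copied across and not replaced.

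Because the physician chooses the dose within the hard constraints, each row is meant to act as a ceiling. A ceiling far above any dose the plan is likely to give to rib does no work. Ribs can lie near the target: Section 5.2 provides for thoracic patients, and Section 5.1.3 allows transverse processes in the CTV with a PTV margin of generally 3 to 7 mm.

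The plan's other safeguards would not obviously catch the error. The QA in Section 5.1.7 checks the dose calculation and plan integrity; it is not described as testing whether a limit is the right one. Section 5.6 provides a single visit at 3 months, and Section 7 leaves grade 1–2 events off the toxicity form.

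**Working it through.** The plan gives no derivation of the rib limit, so there is no figure to reproduce. The check compares the two tables, then sets the rib limits against the prescription.

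**1. Table A against Table B.** Organs are matched by name. The ratio is the Table A limit divided by the Table B limit. For point doses, Table A's limit at <0.03 cc is compared with Table B's maximum point dose.

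| Organ | Table A (Gy) | Table B (Gy) | Ratio |
|---|---|---|---|
| Spinal cord | 17 | 28 | 0.61 |
| Cauda equina | 17 | 31.5 | 0.54 |
| Sacral nerves / plexus | 26 | 32 | 0.81 |
| Esophagus | 20 | 35 | 0.57 |
| Brachial plexus | 21.5 | 32.5 | 0.66 |
| Rectum | 20 | 55 | 0.36 |
| Trachea | 20 | 40 | 0.50 |
| Stomach | 20 | 35 | 0.57 |
| Duodenum | 20 | 26 | 0.77 |
| Small bowel | 20 | 32 | 0.63 |
| Large bowel | 20 | 40 | 0.50 |
| Skin, <10 cc | 20 | 36.5 | 0.55 |
| Kidneys, mean | 6 | 18 | 0.33 |
| **Rib, <5 cc** | **45** | **45** | **1.00** |
| **Rib, second figure** | **57** | **57** | **1.00** |

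Lungs and liver are also in both tables, but their limits take different forms and cannot be paired. That makes 16 shared organs, of which only rib is unchanged. Skin is the closest comparator because it keeps the same volume in both tables.

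Two further signs lie within Table A. The other 14 values in its dose column run from 17 to 26 Gy. Every other entry under *Other* is a dash or a named mean-dose or volume-at-dose limit.

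**2. Rib limits against 24 Gy in 2 fractions.**

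- Share of prescription: 45/24 = 1.875 (188%); 57/24 = 2.375 (238%).
- Per fraction, by the division rule in Section 5.1.5: 45/2 = 22.5 Gy and 57/2 = 28.5 Gy, against 24/2 = 12 Gy prescribed.
- The documents state no hot-spot limit, so 110% to 150% is assumed: 24 × 1.10 = 26.4 Gy and 24 × 1.50 = 36.0 Gy, both below 45 and 57.
- Prescription at which the row first binds under the same hot spots: 45/1.5 = 30.0 to 45/1.1 = 40.9 Gy for the volume limit; 57/1.5 = 38.0 to 57/1.1 = 51.8 Gy for the point limit.

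**3. Illustration of scale only, not a proposed limit.**

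- Skin ratio: 45 × 20/36.5 = 24.7 Gy, and 24.7/24 = 103% of prescription.
- Linear-quadratic conversion, BED = D(1 + D/(n·α/β)), with α/β assumed. At α/β = 3, 45 Gy in 5 fractions gives 45 × (1 + 9/3) = 180. Solving D(1 + D/6) = 180 gives D = 30.0 Gy in 2 fractions, or 125% of 24 Gy. For α/β of 2 to 5, D is 29.5 to 30.8 Gy (123% to 129%).
- The same conversion of 57 Gy gives 37.6 Gy at α/β = 3 and 37.1 to 38.5 Gy for α/β of 2 to 5.
- Delivered in 2 fractions, 45 Gy has a BED of 45 × (1 + 22.5/3) = 382.5 at α/β = 3, which is 382.5/180 = 2.1 times that of 45 Gy in 5 fractions.

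**The case against.** The strongest reply is that correcting the row might change little. A same-BED volume limit is 123% to 129% of 24 Gy, while the undisputed Table B row is 45/35 = 129% of its own 35 Gy. The corrected row would therefore be about as slack as the 5-fraction one. A same-BED point limit of 37.1 to 38.5 Gy lies above the largest assumed hot spot, 36.0 Gy. Only the skin scaling brings the limit close to prescription, and nothing in the documents supports moving a ratio from skin to rib. Table B also has limits above its prescription that nobody would call errors, such as great vessels at 47 and 53 Gy.

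This stands as a caution about size. At 24 Gy the practical effect may be small, and the per-fraction figures are ceilings, not expected doses. But 24 Gy is only suggested, and the printed row is slack well beyond it. The evidence of error is the duplication, not that the limit exceeds prescription.

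Some matches are approximate: Table A's cord and cauda equina are PRV structures, sacral nerves are paired with sacral plexus, and trachea with trachea and large bronchi. Without those four, nine pairs remain, all lower in Table A, at 0.33 to 0.77. The pattern holds.

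It is also true that the approved 2-fraction limit is not in the documents. The duplication is certain; the carry-over is an inference, though a well-supported one. Damage in text extraction is an unlikely explanation, because the neighbouring Table A rows are intact and carry 2-fraction values.

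**Conclusion.** The concern holds and should be fixed. The 2-fraction rib constraint equals the 5-fraction one on both figures, against a pattern in which every other comparable limit is lower. A carried-over row is the only reading the text supports well. As printed, the limits are 188% and 238% of the suggested 24 Gy. They would not bind there if rib hot spots stay within the assumed 110% to 150%; the volume limit would first engage at a prescription of 30.0 to 40.9 Gy.

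The scope is narrow: rib safety in 2-fraction courses with ribs near the target. The cord limits, the first-fraction feasibility endpoint and the goal of 10 evaluable patients are unaffected. Whether a corrected limit would bind at 24 Gy cannot be settled from the documents; the illustrations run from 103% to 129% of prescription for the volume limit.

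**What to change.** Check the Table A rib row against the constraint set that Section 5.1.6 describes as already approved for routine clinical use. Replace it with that set's 2-fraction rib limit, labelling the volume limit and the point-dose limit separately. If the set has no 2-fraction rib limit, remove the row. Carry the change into the planning template and re-check any 2-fraction plans already accepted against the corrected value.

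The cost is a one-row protocol amendment, a template update and a review of existing 2-fraction plans. No new data or patients are needed.

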5.1.6 Adaptive Treatment Planning at Subsequent Fractions

After delivery of the first treatment fraction using a same-session MR-only simulation and treatment with SMART, the treating physician will evaluate the patient's individual anatomy at subsequent treatment fractions to determine if further daily adaptive planning is indicated. Treatment plan re-optimization will be performed for dose adaptation if it is determined that the patient's anatomy necessitates dose adaptation with the goal of sparing of normal structures (i.e., not violating the predetermined hard constraints based on safety constraints that are already approved of for routine, clinical use).

5.1.7 Quality Assurance of the Adaptive Plan

Patient specific QA will be performed at each fraction prior to delivery of the adaptive treatment plan. Given that dose measurements will not be possible with the patient on the table, this will be achieved by performing our standard process of an independent Monte Carlo dose calculation on the image of the day, using the exported beam parameters, and mapped electron density. The independently calculated dose distribution will be compared to the dose distribution exported from the MRIgRT system, looking at dose volume histograms and 3D gamma analysis of all voxels within the patient. In addition, in-house plan integrity verification software will be utilized to evaluate plan quality and integrity via plan parameters including contours, beam angles, segments, and monitor units. After completion of the automated checks, a final review by physics will be required prior to proceeding to treatment delivery.

5.2 Collection of AEs

For all patients, neurologic toxicities of concern include (but are not limited to) treatment-related spinal injury resulting in sensory alteration, muscle weakness, or neuropathic pain limiting self-care in activities of daily living. For patients receiving treatment to lower thoracic and lumbar spine sites, toxicities of concern also include (but are not limited to) gastrointestinal toxicities such as: severe pain, severe nausea or diarrhea, severe constipation, and/or gastrointestinal hemorrhage, stenosis, ulceration, fistula, perforation, etc. Patients undergoing treatment for thoracic metastases will additionally be assessed using the CTCAE v5.0 criteria for lung, esophageal (eg esophagitis), and cardiovascular toxicity. Regardless of treatment site, skin toxicity will be tabulated according to the CTCAE v5.0 criteria.

5.3 Definitions of Evaluability

Endpoint	In order to be evaluable for this endpoint, a patient must have...
Primary: Feasibility	Received simulation
Exploratory: Time from consult to delivery of first fraction	Had a consult and received at least 1 fraction of RT
Exploratory: Local, in-field tumor response rates at 3 mos	Received any study treatment and undergone volumetric imaging at 3 mos
Exploratory: Local, in-field tumor control rate at 3 mos	
Exploratory: Grade 3 or higher toxicity	Received any study treatment
Exploratory: Dosimetric differences between MRI-only planning using standard bulk density override dose calculations and voxel-by-voxel MRI-based dose calculation using MLA	Received MRI and dose calculated using bulk density vs voxel-by-voxel
Exploratory: On-table time required for initial treatment fraction and subsequent treatment fractions	Received at least 1 fraction of RT

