1.5 Rationale

In light of our increasing experience with MRgRT and adaptive planning and advances in MR-only planning, we propose here to evaluate the feasibility and safety of same-session MR-only simulation and treatment with SMART for spinal metastases. Although spine SBRT is a standard-of-care treatment modality, this expedited same-session MR-only simulation and treatment with SMART workflow is novel. Previously, delivery of spine SBRT has typically required several days from time of consultation to simulation and then 1-2 weeks from simulation to the initiation of treatment. On this proposed study, patients will not undergo CT simulation and will instead have same-session MR-only simulation

and treatment planning, on-table, using SMART. In this manner, patients would initiate treatment within just several days from the consult. Feasibility of the workflow will be defined as successful delivery of the first fraction of same-session MRI-only simulation and treatment with SMART on the first on-table attempt for at least 70% of patients. Patients will be treated in either a two or five fraction course over 1-2 weeks. Although our long-term goal will be to achieve a significantly shortened time from consult to treatment as compared to traditional SBRT using simulation, the present study will be driven by short-term goals of workflow feasibility and safety.

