2 OBJECTIVES AND ENDPOINTS

Objectives	Endpoints	Justification for Endpoints
Primary		
Demonstrate that same-session MRI-only simulation and treatment with stereotactic MRI-guided radiotherapy (SMART) for spinal oligometastases is feasible by confirming that the first fraction of same-session MRI-only simulation and treatment with SMART can be delivered on the first on-table attempt for at least 70% of patients.	Delivery of the first fraction of same-session MRI-only simulation and treatment with SMART within the first on-table attempt for at least 70% of patients.	Clinically relevant
Exploratory		
1. Determine the average time (days) from patient consult appointment to successful delivery of the first treatment fraction.	Average time (days) from patient consult appointment to successful delivery of the first treatment fraction.	Clinically relevant
2. Determine the local, in-field tumor response and control rates at three months.	Local control rate Local in-field tumor response	Clinically relevant
3. Demonstrate that same-session MR-only simulation and treatment with SMART for treatment of spinal metastases will lead to comparable toxicities compared with historically reported rates using standard, CT-based SBRT assessed prospectively at three months post-treatment and retrospectively for later time-points.	CTCAE version 5, treatment related Grade 3 or higher toxicities	Clinically relevant
4. Determine the projected dosimetric differences between the study method of MRI-only planning using standard	Dosimetric differences between MRI-only planning using standard bulk density	Generation of preliminary data for

bulk density override dose calculations (which will be clinically used for all patients) and an exploratory alternative method of a novel voxel-by-voxel MRI-based dose calculation using an institutionally developed machine learning algorithm (which will be simulated for comparison but not used in clinical treatment planning).
	
override dose calculations and voxel-by-voxel MRI-based dose calculation using MLA
	
future radiation planning techniques.

5. Determine the on-table time required for same-session MR-only simulation and treatment with plan generation for the initial treatment fraction and for subsequent treatment fractions.
	
On-table time required for initial treatment fraction and subsequent treatment fractions
	
Clinically relevant

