3.2 Exclusion Criteria

1. Past history of radiotherapy within the projected treatment field to be treated by MRI-guided SBRT
2. Medical contraindication to undergoing MR imaging.
3. Spine metastasis resulting in symptomatic spinal cord compression.
4. Any other condition that, in the opinion of the treating radiation oncologist, renders the patient unfit for SBRT.
5. Pregnant and/or breastfeeding. Women of childbearing potential must have a negative pregnancy test within 14 days of study entry.

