5.5 Duration of Therapy

If at any time the constraints of this protocol are considered to be detrimental to the patient's health and/or the patient no longer wishes to continue protocol therapy, the protocol therapy should be discontinued and the reason(s) for discontinuation documented in the case report forms.

In the absence of treatment delays due to adverse events, treatment may continue for a total of 2 or 5 fractions of SBRT or until one of the following criteria applies:

- Documented and confirmed disease progression
- Death
- Adverse event(s) that, in the judgment of the investigator, may cause severe or permanent harm or which rule out continuation of study drug
- General or specific changes in the patient's condition render the patient unable to receive further treatment in the judgment of the investigator
- Suspected pregnancy
- Serious non-compliance with the study protocol
- Lost to follow-up
- Patient withdraws consent
- Investigator removes the patient from study
- The Siteman Cancer Center decides to close the study

Patients who prematurely discontinue treatment for any reason will still be followed as indicated in the study calendar.

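### The denominator of the primary feasibility rate depends on a step of the attempt being judged, so a patient placed on the table but never simulated is left out rather than counted as a failure (minor)

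*Combined protocol and SAP*

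**What the plan says.** All references are to the combined protocol and SAP.

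- **Endpoint.** Section 2 sets the sole primary endpoint: the first fraction is to be delivered "within the first on-table attempt for at least 70% of patients". Section 12.3 repeats the 70% figure. Together with safety and efficacy, it is the basis for recommending wider study.
- **Who counts.** The table in Section 5.3 admits a patient to this endpoint if they "Received simulation". For the dosimetric endpoint the same table says "Received MRI and dose calculated using bulk density vs voxel-by-voxel". It does not say whether receiving simulation and receiving MRI differ.
- **What simulation is.** Section 1.5 says that "patients will not undergo CT simulation and will instead have same-session MR-only simulation". Section 5.1.4 says that on treatment day one "another volumetric MRI image will be obtained on the treatment machine itself". The earlier step, which uses a "diagnostic MRI volumetric image set obtained prior to study enrollment", is called a pre-plan, not simulation.
- **Accrual and replacement.** Section 12.2 sets a goal of 10 evaluable patients, chosen on clinical grounds and not on power. The Response table in Appendix E has a column for whether the patient was replaced. No section says who may be replaced or why.
- **Not defined.** The documents do not say when an on-table attempt begins, or whether an MRI that is started and abandoned counts as simulation.

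**The concern.** A feasibility rate should have in its denominator everyone in whom the procedure was tried. Here the entry condition is met only during the procedure. A patient who is positioned on the table and leaves before the MRI is obtained (for example, unable to tolerate positioning, or because of a scanner fault) has not had the first fraction delivered at the first attempt. Under Section 5.3 as written, that patient is outside the rate.

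Every patient lost in this way is a non-delivery, so the omission cannot lower the reported rate. With 10 patients and a benchmark of 7, one such patient can decide a borderline result. Because the key terms are undefined, the classification could also end up being made after the outcome is known.

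**Working it through.** **Step 1. Set the sections side by side.** Four situations are possible for a patient placed on the table for the first session.

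| What happens | Evaluable under 5.3? | Counted as |
|---|---|---|
| MRI obtained, fraction delivered in that session | Yes | Success |
| MRI obtained, fraction not delivered (planning, QA, table time) | Yes | Failure |
| No MRI at the first session, simulated at a later one | Yes | Failure (not the first attempt) |
| No MRI, then or later | No | Not counted |

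Only the last row is at issue. If an abandoned MRI counts as simulation, that row shrinks to patients never imaged at all.

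**Step 2. The benchmark.** The plan gives no alpha, power or null rate, so there is no sample-size figure to reproduce. Applied to the goal of 10 evaluable patients, 70% means at least 7/10. The exact (Clopper-Pearson) 95% interval for 7/10 is 34.8% to 93.3%.

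**Step 3. Put the missing patients back.** Let x be the successes among 10 evaluable patients, and k the never-simulated patients met before the tenth evaluable one. This takes accrual as continuing to 10 evaluable patients.

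*Counting everyone placed, x/(10 + k):*
- x = 7, k = 1: 7/11 = 63.6%, below 70%.
- x = 8, k = 1: 8/11 = 72.7%, still passes.
- x = 8, k = 2: 8/12 = 66.7%, below 70%.

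*Counting the first 10 placed, with patient order exchangeable:*
- x = 7, k = 1: the tenth evaluable patient drops out of the count and is a success with probability 7/10. The result is 6/10 with probability 0.70 and 7/10 with probability 0.30.
- x = 8, k = 1: 7/10 with probability 0.80 and 8/10 with probability 0.20. Both pass.
- x = 8, k = 2: the eleventh patient placed is evaluable with probability 9/11. Two evaluable patients then drop out, and both are successes with probability (8/10)(7/9) = 0.622. So 6/10 has probability (9/11)(0.622) = 0.509. The remainder is 7/10 (0.436) or 8/10 (0.055).

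*If nobody is replaced:* with 10 placed, 6 successes and one never simulated, the rate is 6/9 = 66.7%, which still misses 70%. The single-case reversal therefore depends on accrual continuing to 10 evaluable patients.

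**Step 4. Effect on the chance of meeting the benchmark.** Let p be the true success rate among all placed and q the never-simulated rate. The rate among evaluable patients is p/(1 − q), and the chance of meeting the benchmark is P(X ≥ 7) for n = 10. The documents give no value for p or q, so all values below are assumptions.

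| p | q = 0 | q = 2% | q = 5% | q = 10% |
|---|---|---|---|---|
| 60% | 38.2% | 41.3% | 46.4% | 55.9% |
| 65% | 51.4% | 55.0% | 60.7% | 70.8% |

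For example, p = 0.60 and q = 0.05 give 0.60/0.95 = 0.632, and P(X ≥ 7) = 46.4%. Further from the benchmark the effect of a small q fades: at q = 2% the rise is 3.1 points for p = 60%, 2.7 for 80%, 1.6 for 85% and 0.7 for 90%.

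The chance of at least one such patient among 10 placed, 1 − (1 − q)^10, is 18.3%, 40.1% and 65.1% for q = 2%, 5% and 10%.

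**The case against.** The strongest reply is that the affected group is very small, and much of this stands. The novel risks of the workflow (on-table planning, density assignment, QA and time on the table) mostly arise after the MRI, and those failures already count. So does a patient simulated only at a later session. Section 3.2 excludes anyone with a "Medical contraindication to undergoing MR imaging", and Section 5.1.4 expects each patient to have had a diagnostic MRI, although Section 3.1 requires only a diagnostic CT. The row in Section 5.3 is also broader than the rows for time to treatment and on-table time, which require a delivered fraction.

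A second reply is that such a patient would not be hidden. Section 5.5 asks for "the reason(s) for discontinuation documented in the case report forms", and the Appendix E Response table could show the patient as not delivered at the first attempt. That also stands, but neither record puts the patient in the denominator.

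A third is that replacement rests on thin evidence: an accrual goal and one column heading in a blank monitoring table. Appendix E is not a dependable guide to the rules, since it answers No on early stopping rules while Section 12.1 sets some. This is accepted, and replacement is treated here as an inference. Finally, the 70% figure is a descriptive benchmark in a pilot and not a formal test, so the pass probabilities above are illustrations, not operating characteristics that the plan claims.

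Two stronger readings are tempting. A reader might infer that the rule lets first-session failures in general be discarded; the table in Step 1 shows that it does not. A reader might also infer that the plan replaces failed patients as a matter of policy; no section says so.

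**Conclusion.** The point holds in a narrow form. Section 5.3 states a denominator rule that depends on part of the outcome, and no other section counts an on-table, never-simulated patient as a failure. Leaving such a patient out moves the result upward or leaves it unchanged. One case can change the conclusion at a reported 7/10. One case behind 8/10 still passes, and two may not.

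This rests on reading simulation as the first-session on-table MRI, which Sections 1.5 and 5.1.4 support although the term is never formally defined. The single-case reversal also rests on accrual continuing to 10 evaluable patients. How often such patients occur cannot be judged from the documents; the rates of 2% to 10% are illustrative. The documents do not support a claim that the feasibility result will be materially inflated.

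Severity: minor. It affects the only primary endpoint, but few patients, and a change of wording removes it.

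**What to change.** **Section 5.3.** Define evaluable for feasibility as every registered patient placed on the MR-linac table for the planned first session. Define that session as the first attempt, and count non-delivery in it as a failure with the reason listed. Show machine faults separately, since whether they count against the workflow is a matter of judgement.

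**Replacement.** State a rule, limited to patients who never reach the table, and list those patients with reasons.

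**Section 12.3, alongside.** Report x/n with its exact 95% interval, and describe 70% as an observed go-forward benchmark rather than a confirmed rate. This is good practice at n = 10 and is not needed to establish the evaluability point.

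**Cost.** Wording only, with no extra patients or procedures. The Appendix E Response table already has columns for first-attempt delivery and replacement. The downside is that the reported rate may be slightly lower, and a fault before imaging will appear as a failure unless the listed reason is read with it.
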